D.3.b. MNA Identification Phase: Subjects will be shown how MedMinder™ works and demonstrate proficiency in loading and activating the device. They will be told their doctors will receive summary reports on their med intake patterns. The tray plugs into a standard 110v outlet, has 28 compartments allowing up to 4 dose times per day for 7 days, and is capable of providing escalating reminder signals (described in D.5.a). **Reminder functions will be disabled for the 1-month screening phase.** The nurse manager (or project manager, [name]) and subject will program the MedMinder for dosing times (example of subject's 24-hr MedMinder activity in Appx. 23). Subject will receive written and oral instructions on MA criteria (i.e., all meds taken within 180 min window centered on prescribed dosing time). SMASH app has auto call feature for TACHL service line for technical issues. Time and date stamped opening and closure of the tray's compartments are relayed via GSM wireless cellular transmitter/receiver to MedMinder™ server for processing. The encrypted data are sent to a HIPPA-compliant server database housed in the TACHL center. The MA formula will be used to calculate MA scores.^{22,23,52,121} (see Appx. 2) **Only subjects with MA score < 0.85 over the 4 week screening and whose subsequent resting and 24-hr SBP evaluations reconfirm uncontrolled HTN will be eligible for enrollment into the RCT.** [name] will randomly assign the 8 sites to either SMASH or

enhanced SC conditions.

D.4. Time Table (Table 2) Based on our SMASH trials, we will recruit 16 subjects/mo beginning mo 4 and finish recruiting by mo 15. We will provide a smart phone and/or service plan for ~40 SMASHers we project might lose phones or service plans during the trial.^{20,21,25,27} Post-trial data collection will finish in mo 34. Post study focus groups and subsequent qualitative analyses will end in mo 43. Table 2 presents a timetable for the study.

Activity	Month
Set-up	Mos 1-3
Recruitment	Mos 4-15
Intervention	Mos 5-22
Follow-up	Mos 16-34
Focus Groups	Mos 35-37
Statistical analyses	Mos 23-28
Prep. and Submission of Effectiveness RCT RO1	Mos 36-42
	Mos 43-48
Month	0 2 4 6 8 10 12 14 16 18 20 22 24 26 28 30 32 34 36 38 40 42 44 46 48
Year	1 2 3 4

D.5. SMASH Protocol:

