D.10. Quantitative Analyses: AIM1 Primary outcome measures are % of subjects with >0.90 MA from MedMinder and % within JNC8 clinic resting BP guidelines (<140/90 mmHg). Secondary analyses will assess resting & ambulatory BP levels (e.g., 24-hr, daytime/nighttime BP level changes) & MA indices (i.e., MPR score changes). Intent-to-Treat (ITT) sample analyses will be used along with multiple imputation methods for missing end-of-study outcomes.^{149,150} To assess relationships between intervention outcomes and intervention status (SMASH or SC) at end of the active trial period (6-mo visit, primary endpoint), two-sided Cochran-Mantel-Haentzel chi-square tests for unadjusted differences in proportions will be used. Adjusted differences in proportions at the 6-mo visit will be compared using logistic regression. To assess relationships over time, we will use a generalized linear mixed models (GLMM; generalized estimation equation [GEE]-type models) analytic model with group (SMASH vs SC) & time (3, 6, 12 & 18 months) included as fixed effects and FQHC practice site as a random effect to account for clustering within FQHC practice site/MD.¹⁵¹⁻¹⁵³ In the first set of models, baseline measurement of the dependent variables (e.g., MA or BP levels) will be included as adjustment variable. The test of primary interest is F-test for the treatment x time interaction, which will reflect a difference in change between the 2 groups over the study. If a statistically significant treatment x time

interaction is found, we will obtain odds ratios for SMASH vs SC groups at each of the study time points.

A mixed effects model (MEM) will be used to compare the primary continuous outcome measures (e.g., tray or MPR derived MA scores or BP levels) for the two groups over the study period. Modeling will be carried out as described above. We will estimate resting and 24-hr BP changes and MA (MPR) changes for each subject over the trial (baseline, 3, 6, 12 & 18 months) and the within subject longitudinal trajectories (e.g., slopes) and summarize as the mean longitudinal trajectory within each group. ICCs and variance estimates will be obtained of efficacy outcomes and covariance structure of the longitudinal scores for determination of sample size (and hence adequate power) for a future effectiveness RCT.

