In determining eligibility and subsequent enrollment, participants will have their resting BP measured by a research technician during an initial screening visit. If their average of the final 2 SBP readings \geq 140 mmHg and their 24-hr SBP \geq 130 mmHg, they will be eligible for the 1-month MA screening using the electronic medication tray with its reminder functions disabled. If, at the end of the 1-month MA screening, the adherence score is $<$ 0.85, they will participate in a baseline study evaluation that will again include measurement of resting BP and 24 hour BP. Those who again have uncontrolled HTN (resting SBP \geq 140 mmHg and 24-hr SBP \geq 130 mmHg) will be eligible for participation in the trial. Participants will have the resting BP and 24-hr BP monitoring performed again at months 3, 6, 12, and 18. At each evaluation, participants will complete a battery of questionnaires that have been purposely selected as having established psychometric properties for AAs and the age range of our cohort (see Appx 1, 7-21 for copies of questionnaires and additional psychometric properties than those presented in Table 3). Questionnaires will include measures of self reported MA, competence, autonomous motivation, health literacy, HTN knowledge, adverse events, med side effects, depression, sleep quality, stress, quality of life, patient satisfaction with provider). They will also complete several scales that assesses degree of satisfaction with study implementation and study/home evaluations, usability of the SMASH protocol ,app and wireless BP device or the enhanced SC group's educational materials, and potential barriers/facilitators of adherence. As part of standard care, all participants will have blood drawn at baseline and months 6, 12 and 18 to include TC, LDL, HgA1c and blood glucose levels. All subjects will wear an ambulatory BP monitor for 24-hr on several occasions over the course of the study. The combination of anthropometric evaluations, resting BP measurements, ambulatory BP measurements, and the majority of the questionnaires has been used in prior studies (e.g., HL 05662, HL 078216, and SMASH feasibility RCTs) and was not considered a burden by the subjects. All study materials will be de-identified so that only the subjects ID number will be associated with any collected data.

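### The treatment-by-time test for BP control only asks whether the SMASH v SC odds ratio changes after month 3, so the month 12 and 18 odds ratios tied to it are least likely to be produced when the benefit persists

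*Combined protocol and SAP*

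**What the plan says.** D.10, AIM 1 uses a GLMM/GEE-type model to assess the binary outcomes over time, with "group (SMASH vs SC) & time (3, 6, 12 & 18 months) included as fixed effects" and practice site as a random effect. Baseline is handled as follows in the models fitted first: "baseline measurement of the dependent variables (e.g., MA or BP levels) will be included as adjustment variable". On testing, D.10 states that "The test of primary interest is F-test for the treatment x time interaction". It describes that test as one "which will reflect a difference in change between the 2 groups over the study". Visit-specific results are made conditional: if a significant "interaction is found, we will obtain odds ratios for SMASH vs SC groups at each of the study time points". The same section does not say what is reported if the interaction is not significant. The group term is in the model but is not named as a test.

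Eligibility fixes the binary outcomes at baseline. D.3.b admits "Only subjects with MA score < 0.85 over the 4 week screening and whose subsequent resting and 24-hr SBP evaluations reconfirm uncontrolled HTN". Protection of Human Subjects, section 1.b, describes that visit: "they will participate in a baseline study evaluation that will again include measurement of resting BP and 24 hour BP". Entry requires resting SBP of at least 140 mmHg, 24-hr SBP of at least 130 mmHg and a tray score below 0.85.

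Two other places matter. D.12 says that the purpose of follow-up without booster sessions is to learn whether six months of SMASH gives lasting improvement. Table 3 collects the medication tray daily for six months only. The month 6 primary analyses (Cochran-Mantel-Haenszel and logistic regression) stand apart from this model.

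**The concern.** A reader would take the description of the interaction to mean a comparison of change from baseline. With baseline outside the time factor, any benefit already present at month 3 goes into the group main effect, and the interaction sees only what happens afterwards. Making baseline a fifth time level would not rescue the binary model: BP below 140/90, 24-hr BP below 130/80 and tray adherence above 0.90 are all 0% in both arms at entry, so the baseline log odds cannot be estimated.

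At stake is the persistence question in D.12. An early benefit that is then kept is also what the pilot data suggest. In the FQHC feasibility trial (C.1.4), 90-100% of SMASH v 25-40% of SC patients were controlled at both months 3 and 6. If that continued to month 18, the comparison that answers D.12 would depend on a test with no sensitivity to it.

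**Working it through.** **Inputs from the plan.** Four clinics per arm with 22 patients each: 4 x 22 = 88 per arm and 176 in total, which matches D.8. Two-sided alpha is 0.05, the site ICC is 0.04, and the difference is 30 points or more. D.8 gives no power for the interaction, so there is no stated figure to reproduce.

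**Assumptions.** D.8 does not state the two rates. I take SC 30% and SMASH 60%. Within-patient correlation rho is that of a latent normal variable, at 0.3, 0.5 and 0.7. (D.8 mentions correlation up to 0.5, for continuous outcomes.)

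**Method.** Let OR_j be the odds ratio at visit j, and let d hold log OR_6 - log OR_3, log OR_12 - log OR_3 and log OR_18 - log OR_3. The 3-df Wald statistic has noncentrality lambda = d' Var(d)^-1 d. It rejects when a noncentral chi-square on 3 df exceeds 7.815.

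**Constant odds ratio.** OR = (0.60/0.40)/(0.30/0.70) = 3.5 at every visit. Then d = 0 and lambda = 0, so rejection is 0.050. The same holds for 10% v 90% (OR = 81 throughout). Neither effect size nor rho enters.

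**Other patterns** (months 3, 6, 12, 18):

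| Pattern | SMASH % | SC % | Odds ratios | Rejection at rho 0.3 / 0.5 / 0.7 |
|---|---|---|---|---|
| Constant odds ratio | 60, 60, 60, 60 | 30 throughout | 3.5 throughout | 0.050 / 0.050 / 0.050 |
| SMASH still rising at month 3 | 50, 60, 60, 60 | 30 throughout | 2.33, 3.5, 3.5, 3.5 | 0.154 / 0.178 / 0.222 |
| SC rises after month 6 | 60, 60, 60, 60 | 30, 30, 40, 40 | 3.5, 3.5, 2.25, 2.25 | 0.229 / 0.269 / 0.342 |
| Benefit halved after month 6 | 60, 60, 45, 45 | 30 throughout | 3.5, 3.5, 1.91, 1.91 | 0.398 / 0.468 / 0.580 |
| Benefit fades to nil by month 18 | 60, 60, 45, 30 | 30 throughout | 3.5, 3.5, 1.91, 1.0 | 0.853 / 0.909 / 0.960 |
| Benefit lost after month 6 | 60, 60, 30, 30 | 30 throughout | 3.5, 3.5, 1.0, 1.0 | 0.961 / 0.982 / 0.994 |

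**Check with clustering.** A simulation with 4 clinics of 22 per arm, latent site ICC 0.04 and 6,000 trials gave 0.049 / 0.055 / 0.055 for the constant odds ratio and 0.957 / 0.982 / 0.995 for the lost benefit.

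**What a direct contrast at one visit would have.** Variance inflation is 1 + 21 x 0.04 = 1.84. For 60% v 30%, SE = sqrt(1.84 x (0.24 + 0.21)/88) = 0.097 and 0.30/0.097 = 3.09. Power is about 0.73 with a t reference on 6 df (8 clinics less 2), against 0.05 for the interaction when the odds ratio is constant.

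**The case against.** The strongest reply is that any test of whether an effect changes should reject at alpha when it does not change. With no interaction, an analyst would ordinarily read the group term, and under a constant odds ratio that one estimate covers months 3 to 18. Most of this stands. The group effect is estimable, so one may not infer that the plan is unable to show a held benefit. What is missing is a statement that the group term, or any contrast at months 12 and 18, will be tested or reported.

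A reader might also infer that odds ratios are obtained only if the test is significant. The text says if; it is silent on the other case.

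A reader might take 5% to cover every kind of held benefit. It does not. It needs the same odds ratio at all four visits, and the table shows about 15 to 35% under two ordinary departures. It also needs the model to handle repeated measures within patients. D.10 names only practice site as a random effect. In a check that ignored within-patient correlation, rejection fell to 0.0075, which does not help the plan.

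Other analyses do reach month 18: the moderator models, the structural equation models, the mean trajectories within each group, and the powering for sustained 24-hr BP control. So durability does not rest on this test alone. None of them, however, states a SMASH v SC comparison of resting BP control at month 12 or 18.

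Finally, it is tempting to extend the point to the continuous and AIM 2 and 3 models. The documents do not support that as an error. Modelling is to follow the description above, but the plan also estimates "changes for each subject over the trial (baseline, 3, 6, 12 & 18 months"), so whether baseline is a time level is unclear.

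**Conclusion.** The point holds for the binary longitudinal model of BP control. The test named as being of primary interest measures change in the odds ratio after month 3, and the plan's description of it is misleading. Rejection is 5% for a constant odds ratio at any effect size, about 15 to 35% under the two departures examined, and about 96 to 99% if the benefit is lost after month 6. The planned comparison at months 12 and 18 is thus least likely to follow when the benefit persists.

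The 5% rests on a constant odds ratio and on modelling within-patient correlation. The other figures rest on the assumed 30% v 60%, the assumed patterns and rho of 0.3 to 0.7. The month 6 primary endpoint is not touched, so this should be fixed but does not threaten the main result. For tray adherence above 0.90 the question does not arise at months 12 and 18, because Table 3 provides no tray data then.

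**What to change.** In D.10, AIM 1:

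- Pre-specify SMASH v SC odds ratios with confidence intervals for BP control at months 12 and 18, and report months 3 and 6, whatever the interaction shows. Use inference that allows for eight clinics and for repeated measures within patients.
- Keep the interaction as a secondary test and describe it as testing whether the effect changes after month 3.
- Fit tray adherence above 0.90 at months 3 and 6 only, and use MPR, already collected to month 18, for adherence in follow-up.
- As a clarification, state for the continuous and AIM 2 and 3 models whether baseline is a covariate or a time level, and whether the same reporting rule applies.

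Leave the month 6 primary analyses as they are. The cost is wording in the analysis plan; no extra data are needed.

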D.6. Measures: Table 3 presents all outcome variables, questionnaires and timing of administration. Most scales have been used with 21-59 yr old AAs and have established psychometrics. We provide brief psychometric information (e.g., internal consistency, test-retest reliability) (see Appx.1, 7-21, for copies and additional psychometrics). We will assess SDT constructs (competence/self-efficacy; MA Self-Efficacy Scale [Appx. 7])^{101,123,124} & autonomous motivation [Treatment Self-Reg. questionnaire; Appx. 8],^{97,125} cultural values, beliefs and life goals,¹⁰⁶ (Appx. 14), self-reported MA (Morisky scale, Appx. 1),^{105,126,127} and MPR (formula in Appx.30).¹²⁸ We will assess sociodemographic, biobehavioral and disease attitudes/knowledge variables which have been identified as potential mediators of MA^{7-10,60-68} including HTN knowledge (Appx. 9),^{129,130} health literacy and numeracy (Test of Functional Health Literacy scale, Appx.10),¹³¹⁻¹³³ med side effects (Appx.11),¹³⁴ quality of life (SF-8, Appx 12),¹³⁵ depression symptoms (Beck Depression Inventory, Appx.13),¹¹³⁻¹¹⁵ stress (Perceived Stress Scale, Appx.15),^{136,137} sleep quality (Pittsburgh Sleep Quality Index; Appx 16),^{138,139} perceived disease severity (Illness Perception Questionnaire, Appx.17),¹⁴⁰ and patient satisfaction with MD (Quality MD/Patient Interaction, Appx.18).¹⁴¹ These questionnaires will be given at baseline and mos 3, 6, 12 and 18. Satisfaction and usability scales will be completed at mo 6 (System Usability Scale, Telemed. Satisfaction and Usability Scale, Mobile App Rating Scale, Appx. 19-21).¹⁴²⁻¹⁴⁷ All intervention tactics cease for both groups at end of 6-mo trial. Follow-up visits will occur at mos 12 and 18. Per SC, all subjects will have blood drawn for bioassays including TC, LDL, HgA1c and blood glucose at baseline, mos 6, 12 and 18.

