D.12. Potential Problems, Pitfalls & Solutions: A potential problem for any RCT is subject recruitment & retention. The FQHC network identified 2,619 21-59 yr old AAs with uncontrolled HTN (mean age=45.3 yrs) who meet initial prescreening inclusion criteria. Using a 75% participation rate for screening, as experienced in the FQHC feasibility trial, we project access to ~1,964 AAs with sole diagnosis of uncontrolled HTN. Our SMASH trial which used electronic pill monitoring found 79% had 1 mo adherence score <0.85.^{22,23} Given our 91% minimum acceptance into randomization on our feasibility trials involving AAs, a conservative estimate would give us ~1411 patients. Multiple tactics will be used to foster high retention including obtaining full contact info for subjects' immediate family members and ≥ 2 friends at enrollment and updating every evaluation. Transportation will be provided when needed; project evaluations will be scheduled, whenever possible, on subjects' scheduled clinic visits. Birthday and holiday cards will be sent out and non-study related telephone calls made. **A second issue may be subject "tech-phobia".** Our research with AA HTNs,^{20,21} found little concern regarding use of an electronic tray or automated BP monitor, as they operate similarly to instruments they use (e.g., pill trays; digital BP devices). Our SMASH feasibility trials found high acceptability, satisfaction and adherence to the MedMinder and BP self-monitoring protocols.^{22,23,25,26} Patients will be provided auto call numbers in their SMASH app should they experience technical problems. **A third issue is possible post-trial adherence deterioration.** We elected not to include a booster program or other post trial intervention (e.g., motivational interviewing) as our intent is to determine whether 6 mos of SMASH results in persistent improvements in MA and BP control resulting from increased competence and autonomous motivation. SDT-based behavioral change programs that are typically 3-6 mos have led to lasting changes 1-2 yrs later.^{92,95-97} Tentative support was recently published suggesting sustainability of SMASH program's impact upon MA with a 12-mo post-trial eval of AA kidney transplant patients' medical records.²⁴ Former SMASH patients sustained lower BP levels and better JNC8 designated BP control compared to the SC group. Whether such can be achieved with the SMASH program adapted for a more challenging group of patients, AAs with sole diagnosis of uncontrolled HTN, requires evaluation. If reductions are observed, the future effectiveness RCT will include booster sessions guided by participants' suggestions. **A fourth issue is the MedMinder does not detect pill ingestion.** Although the gold standard for med intake monitoring is biosensor pills (e.g., Proteus), these are not commercially available or financially feasible. Further, a 12-wk trial using the Proteus Digital Health ingestible sensor system verified 99-100% accuracy of pills ingested, but 40% of patients dropped out during the first month due to side effects (i.e., diarrhea, erythema & rash from the on-body sensor patch).¹⁷¹ During weeks 8-12, 61% of the remaining patients required SMS reminders to take their pills. In our feasibility trials, increased BP control mirrored increases in MA suggesting AAs with uncontrolled HTN do not fake pill intake. The proposed efficacy RCT will determine whether this is replicable and if improvements in MA and BP control are sustained over the 6-mo intervention and subsequent 12-mo follow-up. **Finally, we**

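### Continuous BP and MPR outcomes: no month-6 contrast or time coding is specified, and neither the month 0-18 slope summary nor the treatment x time test isolates on-treatment benefit

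*Combined protocol and SAP*

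**What the plan says.** D.10 (AIM 1) places resting and ambulatory BP levels and MPR score changes under secondary analyses. For the continuous measures it states: "A mixed effects model (MEM) will be used to compare the primary continuous outcome measures", and then "Modeling will be carried out as described above". The model above is the one for the binary outcomes. It has group and "time (3, 6, 12 & 18 months) included as fixed effects", practice site as a random effect and baseline as an adjustment variable. Of that model the plan says: "The test of primary interest is F-test for the treatment x time interaction". By-visit estimates are odds ratios, obtained only if that interaction is significant.

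The same paragraph adds that BP and MPR changes will be estimated "for each subject over the trial (baseline, 3, 6, 12 & 18 months", together with "the within subject longitudinal trajectories (e.g., slopes) and summarize as the mean longitudinal trajectory within each group".

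D.6 says: "All intervention tactics cease for both groups at end of 6-mo trial". D.12 lists among the pitfalls: "A third issue is possible post-trial adherence deterioration". It gives persistence of effect as the purpose of follow-up without boosters. A.5 notes that gains in earlier trials often faded once the trial ended.

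**The concern.** The shape that the documents anticipate is not a straight line. In the FQHC pilot (C.1.4, Trial 2), BP control in the SMASH arm was 90-100% at both 3 and 6 months, so benefit is expected early. Treatment then stops, and some fading is foreseen. A line through months 0 to 18 blends efficacy with persistence in one number, and the two off-treatment visits dominate it.

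The interaction test has the opposite weakness. With baseline as a covariate and only months 3-18 as outcomes, it asks whether the group difference changes between visits. A benefit that is present at month 3 and never fades does not change.

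The continuous results could therefore be misread in either direction. A real on-treatment reduction could show as a near-zero slope, and a durable one as a non-significant interaction. The plan names no month-6 mean difference to settle the matter. D.8 also counts months 12 and 18 as intervention time points, which conflicts with D.6; the two need to be reconciled.

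**Working it through.** **Inputs from the documents.** Visits at 0, 3, 6, 12 and 18 months (D.10). From D.8: effect 0.48 SD, i.e. 2.4 to 4.3 mmHg for SD 5 to 9; two-sided alpha 0.05; correlation among repeated measures up to 0.5 (0.5 used); 22 patients x 4 clinics = 88 per arm; ICC 0.04, so VIF = 1 + 21 x 0.04 = 1.84.

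**Assumed.** The retention patterns after month 6, compound symmetry, zero expected difference at baseline, and a normal approximation.

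**The plan's own figure.** A single two-group comparison at 0.48 SD gives 89.0% power with 88 per arm and 91.4% with 96. The stated 90% is reproduced, but with no VIF and no gain from repeated measures.

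**Slope weights.** Mean time = (0 + 3 + 6 + 12 + 18)/5 = 7.8. Sum of squares = 60.84 + 23.04 + 3.24 + 17.64 + 104.04 = 208.8. Months 12 and 18 supply (17.64 + 104.04)/208.8 = 58% of it. Months 3 and 6 have negative weights (-4.8 and -1.8), so more benefit at those visits lowers the fitted slope.

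**Slope x 18** = 18 x sum[(t - 7.8) x difference]/208.8, with d the benefit at month 6:

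| Fraction of d at months 3, 6, 12, 18 | Weighted sum | Slope x 18 |
|---|---|---|
| 1, 1, 1, 1 | +7.80 | +0.67d |
| 1, 1, 0.75, 0.50 | +1.65 | +0.14d |
| 1, 1, 0.625, 0.25 | -1.425 | -0.12d |
| 1, 1, 0.50, 0 | -4.50 | -0.39d |
| 0.5, 1, 0.75, 0.50 | +4.05 | +0.35d |
| 0.5, 1, 0.50, 0 | -2.10 | -0.18d |

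At the planning effect of 2.4 to 4.3 mmHg, row 2 gives an apparent benefit of 0.3 to 0.6 mmHg over 18 months, and row 4 an apparent harm of 0.9 to 1.7 mmHg.

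**Where the slope is zero**, with f the fraction left at month 18:
- Full effect by month 3, drop to f held from month 12: 6.6/14.4 = 0.46.
- Full effect by month 3, linear fade: -6.6 + 4.2(1 + f)/2 + 10.2f = 0, so f = 4.5/12.3 = 0.37.
- Half effect at month 3, linear fade: f = 2.1/12.3 = 0.17.

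**Illustration of the information lost** (75% kept at month 12, 50% at month 18; 0.48 SD; n = 88/1.84 = 47.8 per arm):
- Slope: 0.48 x 1.65/208.8 = 0.00379; SE = sqrt[(2/47.8) x 0.5/208.8] = 0.0100; z = 0.38; two-sided power about 7%.
- Month-6 change: variance 2(1 - 0.5) = 1 in SD-squared units; SE = sqrt(2/47.8) = 0.2045; z = 2.35; power 65%.
- Baseline-adjusted month-6 difference: variance 1 - 0.5^2 = 0.75; power 77%.
- Without the VIF: slope about 8%, month-6 change 89%, adjusted difference 96%.

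**Interaction test, visit categorical:**
- Immediate and fully sustained benefit, months 3-18 as outcomes (3 df): every between-visit contrast of the group difference is zero, so power equals alpha, 5%. If baseline were an outcome instead (4 df), power would be 65% with the VIF and 92% without.
- 50%/0% fade: 63% (3 df) or 76% (4 df) with the VIF; 90% or 97% without. With months 3-18 as outcomes, what it detects is the fade.

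**The case against.** The strongest reply is that a reader who infers that the continuous outcomes rest on one slope has misread D.10. Slopes are introduced with e.g., they describe each group, and changes are estimated in the same sentence. The between-group comparison is the mixed model. Its listed visits and F-test are compatible with categorical time, in which case the interaction test has reasonable power against a marked fade. Group is also a fixed effect, so a difference averaged over visits can be estimated. The primary endpoint is binary, at month 6, with its own tests. C.1.4 and D.12 offer tentative evidence of persistence from the transplant pilot, so fading is not a given.

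All of that stands. A further point also stands: if site enters only as a random intercept, it cancels from within-patient change, so applying VIF 1.84 to slopes and changes is an assumption. This is why results without it are shown.

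What the reply does not supply is a statement of how time is coded, a month-6 contrast for continuous outcomes, or a rule for reporting visit-specific mean differences. If time were linear, the interaction would itself be a slope comparison. If the conditional rule for odds ratios were carried over, visit differences would usually be withheld when benefit is immediate and fully held.

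**Conclusion.** The point holds as a gap in the specification of the secondary continuous analyses that should be closed before analysis. The 0-18 month slope mixes on- and off-treatment time and is strongly diluted by moderate fading (+0.14d against +0.67d for the 75%/50% pattern). The interaction test with baseline as covariate has no power beyond alpha for an immediate, fully sustained benefit. Neither yields the month-6 efficacy difference.

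Two stronger readings are not supported. One is that any fading gives a zero or reversed slope. That needs roughly 17-46% or less of the effect left at month 18, depending on onset and fade; with half left under the 75%/50% pattern the sign is still right. The other is that the plan has 7% power. That figure belongs to a slope test that D.10 does not state, and it illustrates slope against month-6 change only under the assumed retention, compound symmetry and VIF 1.84.

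The slope arithmetic depends only on the visit times and the assumed patterns. The power figures are approximate, and with eight clinics a small-sample correction would lower them. The month-6 primary analysis of adherence and BP control is not affected.

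**What to change.** In D.10, for the continuous outcomes:

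- State that visit is categorical in the mixed model, or that time is piecewise with a knot at month 6.
- Pre-specify the baseline-adjusted SMASH-SC mean difference at month 6, with its confidence interval, as the efficacy contrast, reported whether or not the interaction is significant.
- Report the month 12 and month 18 differences, or the change from month 6 to 18, separately as persistence.
- Label any 0-18 month slope as descriptive.
- Reconcile D.8's description of months 12 and 18 with D.6.

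The cost is SAP wording and a few more reported contrasts. No new visits, data or patients are needed.
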